**Table 1 Recruitment Timetable**

	Year 1	Year 2	Year 3	Year 4	Year 5
Cohort 1 Mepolizumab exposed group	20	40	55	55	30
Cohort 2 Asthmatic comparison group	30	60	83	83	44
Cohort 3 Non-asthmatic comparison group	30	60	83	83	44

### 8.3. Variables

#### 8.3.1. Exposure definitions

*Mepolizumab-exposed cohort:* Exposure is defined as any dose of mepolizumab for any length of time from 8 weeks prior to the first day of the last menstrual period (LMP) through the end of pregnancy, as reported by the mother and validated through medical record review. The 8 week cut-off prior to LMP is based upon the terminal half life of mepolizumab of approximately 20 days (clearance of mepolizumab is based on five half-lives).

Exposure is defined as yes/no in the first trimester of pregnancy for major birth defects as the primary outcome. For this study, first trimester exposure is defined as any dose between eight weeks prior to 1st day of last menstrual period and 13 weeks after 1st day of last menstrual period. However, exposure to mepolizumab in the second (>13 weeks through 26 weeks after 1st day of last menstrual period) and third trimester (>26 weeks after 1st day of last menstrual period) will be considered for those selected major birth defects that are potentially biologically plausibly related to later pregnancy exposures, e.g., craniosynostosis. For spontaneous abortion, the exposure is defined as yes/no in the first 20 weeks' of gestation, and for the other secondary outcomes, exposure is defined as yes/no anytime in pregnancy.

Gestational age is determined by an algorithm using best available information. If the first day of last menstrual period and cycle length is known, and ultrasound measures of dating are not discrepant according to standard conventions depending on the timing of the ultrasound, the menstrual period dating will be used to calculate gestational age. If the menstrual period dating is uncertain or unknown, and an ultrasound is available, the earliest (and therefore more precise) available ultrasound dating will be used. In the event of absence of any information on dating, the delivery record best estimate of gestational age will be used.

In exploratory analyses, duration of mepolizumab use in pregnancy, specific gestational timing, and dose of mepolizumab will be explored. In the asthmatic comparison group, duration of other asthma medications duration use in pregnancy, specific gestational timing, and doses will be explored.

### **8.3.2. Outcome definitions**

*Major Birth Defects:* a major structural defect is defined and classified using the CDC coding manual (<http://www.cdc.gov/ncbddd/birthdefects/documents/MACDPcode0807.pdf>), reported by the mother and validated through the medical record. The CDC coding manual is utilized to classify defects reported through the ongoing population-based Metropolitan Atlanta Congenital Defects Program (MACDP) and is based on agreed-upon criteria by CDC investigators for major structural defects regardless of etiology. Infant medical records are abstracted and reviewed by the study research team leaders. Final validation of the classification of all major birth defects reported in the study will be conducted by a VAMPSS Investigator with expertise in the diagnosis of birth defects.

*Preterm Delivery:* preterm delivery is defined as a spontaneous or induced delivery at <37 gestational weeks, reported by the mother and validated through the medical record. Please refer to Section 8.3.1 for further description of the method for defining gestational age and therefore preterm birth.

*Small for Gestational Age (SGA) Infants:* Live born infants who are  $\leq 10^{\text{th}}$  centile on birth weight for infant sex and gestational age will be considered small for gestational age.

The U.S. Centers for Disease Control and Prevention (NCHS) growth charts will be used for full term infants, and the Britton growth charts will be used for preterm infants (Britton et al, 1993). The outcome of birthweight is reported by the mother and validated through the medical record.

*Spontaneous Abortion:* Spontaneous abortion is defined as spontaneous pregnancy loss prior to 20 weeks' gestation. In this study, since women enrol after recognition of pregnancy, spontaneous abortions are only identified after enrollment in clinically recognized pregnancies. This outcome is reported by the mother and validated through the medical record.

*Stillbirth:* Stillbirth is defined as a fetal death that occurs >20 weeks' gestation. This outcome is reported by the mother and validated through the medical record.

### **8.3.3. Confounders and effect modifiers (Abstraction forms in Annex 2)**

The potential confounders/effect modifiers listed below will be considered in multivariable analyses, as well as others that are relevant to each of the study outcomes:

- Maternal and paternal age
- Previous pregnancy history: gravidity and parity, previous spontaneous abortions and elective terminations
- Maternal and paternal race/ethnicity, education, occupation, socioeconomic status
- Pre-pregnancy body mass index
- Previous preterm delivery
- Previous child with a birth defects
- Maternal conditions: e.g., depression, diabetes (see abstraction forms in Annex 2)
- Maternal exposures: gestational timing and dose of all over-the-counter and prescription medications, including all asthma medications used during pregnancy; vitamin and mineral supplements, herbal products; illnesses; fever; vaccinations
- Prenatal testing: ultrasound and other prenatal tests; timing in gestation and results
- Pregnancy complications: e.g., pregnancy induced hypertension, gestational diabetes
- Maternal lifestyle habits: cigarette smoking, alcohol consumption and illicit drug use

- Asthma related covariates: Asthma Control Test at each maternal interview, years since diagnosis of asthma, hospitalizations or unscheduled asthma visits for asthma exacerbations throughout pregnancy, use of systemic steroids for asthma exacerbations, and classification of asthma severity at enrollment based on women self-reported prescription classified by [GINA \(2016\)](#) guidelines.

Methods for identifying and controlling for these confounders and/or effect modifiers are described in Section [8.7.1](#). The Data Analysis Plan (DAP) will provide greater detail on the definitions of, the identification of and the controlling for confounders and/or effect modifiers.

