## 6. RATIONAL AND BACKGROUND

### 6.1. Background

Asthma is a common, life-long inflammatory disease of the airways that affects children and adults of all ages. It is one of the most common long-term diseases worldwide, and can be life-threatening. The prevalence of asthma in adults in the United States is estimated at 7% ([National Health Interview Survey 2001-2003](#)). Prevalence is higher in females than males and has considerably increased in recent years ([National Health Interview Survey 2001-2003](#)). Symptoms come and go and include shortness of breath, wheezing, chest tightness and cough. The cause of asthma is unknown; however, a family history of asthma, eczema or allergy makes it more likely that an individual will develop asthma.

Although the majority of patients with asthma can be effectively treated with available controller medications, a subset of patients do not adequately respond to current standard therapy. This subset of severe asthma is a heterogenous disease that affects approximately 5-10% of asthmatic patients but is responsible for a disproportionate percentage of the health care costs associated with asthma ([Moore 2008](#); [Godard 2002](#); [Antonicelli 2004](#)). About two-thirds of severe asthma patients are reported to have severe eosinophilic asthma in which their symptoms are associated with too many eosinophils (a type of white blood cells) in the blood and in phlegm in the airways.

Mepolizumab is an interleukin-5 antagonist monoclonal antibody (IgG1 kappa) indicated for add-on maintenance treatment of patients with severe asthma aged 12 years and older, and with an eosinophilic phenotype. It is administered as a 100mg subcutaneous injection given every 4 weeks. In randomized controlled trials mepolizumab has demonstrated about a 50% reduction in asthma exacerbations during the treatment period ([Halder 2009](#)).

The prevalence of asthma and severe asthma in women of child bearing age, coupled with the chronic nature of treatment and the preset periodicity with which mepolizumab is given, makes inadvertent exposure in pregnancy likely. The fact that it is given by injection makes the ascertainment of exposed pregnancies early in gestation and documentation of gestational timing of exposure more feasible than in circumstances

where a drug is taken only as needed and not administered by a health care provider. We therefore propose a pregnancy exposure cohort study to assess the safety of mepolizumab in pregnancy.

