#### **8.4. Data sources**

*Maternal Interviews:* In all three study groups, data are collected by semi-structured maternal telephone interview on two to four occasions during and shortly after completion of pregnancy. The interviews include data on exposure timing, dose, and duration for all medications, including mepolizumab, taken anytime in pregnancy as well as data on a wide variety of confounders (See Section [8.3.3](#)).

For women exposed to mepolizumab or other asthma medications, information on disease severity/symptom control from the Asthma Control Test is obtained directly from the mother at each maternal telephone interview. In addition, information on asthma-related hospitalizations and physician visits is collected at the enrollment interview and each of the subsequent maternal interviews. At the conclusion of pregnancy, regardless of the outcome, participants are interviewed about the outcome including presence or absence of birth defects, pregnancy and infant complications and infant size. At this time point the Asthma Symptom Control test questions are asked again to reflect the last four weeks of pregnancy. In addition, asthma treatment regimen at enrollment according to GINA guidelines will be used to classify disease severity.

*Medical Records:* Mothers are asked to release medical records to the study investigators from their obstetrician or other obstetric provider, specialty care provider such as allergist/pulmonologist, hospital of delivery, pediatrician, and any other health care provider involved in the pregnancy. These records are abstracted and used to validate pregnancy outcomes and when necessary to provide details regarding timing or dose of

mepolizumab and other asthma medications in the absence of clear information from maternal report. Self-reported prescriptions used for GINA classification will be validated with medical record information where available. Pre-defined definitions for each of the study outcomes are used for classification.

Validation of classification of major birth defects, the primary outcome, is conducted periodically and before each annual and final study reports by VAMPSS Investigators, who have the relevant expertise to review the outcomes.

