*Statistical methods*: Descriptive tables will be prepared for characteristics of each of the cohorts in each interim and final report displaying means and standard deviations, or proportions and percentages.

For the primary endpoint of major structural defects and for the secondary endpoint of small for gestational age infants, crude comparisons will be made using exact methods to develop relative risk estimates and their 95% confidence intervals.

For the secondary endpoints of preterm delivery, spontaneous abortion, and stillbirth, survival methods will be used (Kaplan Meier) to estimate crude rates and confidence intervals accounting for gestational timing of enrollment in the study.

Adjusted analyses producing rates and 95% confidence intervals, where numbers permit, will be conducted for major birth defects and small for gestational age infants using logistic regression. Adjusted analyses producing rates and 95% confidence intervals, for preterm delivery, spontaneous abortion and stillbirth, where numbers permit, will be conducted using Cox Proportional Hazards. A minimum of 30 events in the overall analysis sample is required for adjusted analysis for those outcomes assessed with logistic

regression. A minimum of 20 events in the overall analysis sample is required for adjusted analysis for those outcomes assessed with Cox Proportional Hazards.

Confounders will be considered for each adjusted analysis separately, using the method of change in estimate of the effect of exposure to mepolizumab by 10% or more. If one confounder is identified, direct adjustment will be performed. However, given the expected low frequency of events in a study of this size, if two or more confounders are identified in any given analysis, a propensity score approach for adjustment will be considered.

Appropriateness of models will be assessed graphically and by standard statistical methods

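### The candidate confounders include variables that mepolizumab or the outcome can change, and the 10% change-in-estimate rule can select them, mainly in the adjusted SGA and preterm delivery models

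*Protocol*

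**What the plan says.** Section 8.3.3 lists variables to be considered in multivariable analyses. Alongside age, obstetric history, BMI and similar baseline items, it names:

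- "hospitalizations or unscheduled asthma visits for asthma exacerbations throughout pregnancy, use of systemic steroids for asthma exacerbations"
- "Asthma Control Test at each maternal interview"
- "Pregnancy complications: e.g., pregnancy induced hypertension, gestational diabetes"
- "Prenatal testing: ultrasound and other prenatal tests; timing in gestation and results"

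Section 8.4 adds a final ACT at the interview after the pregnancy has ended: "At this time point the Asthma Symptom Control test questions are asked again to reflect the last four weeks of pregnancy". It also states that "asthma treatment regimen at enrollment according to GINA guidelines will be used to classify disease severity".

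Section 8.7.1 chooses confounders for each adjusted analysis "using the method of change in estimate of the effect of exposure to mepolizumab by 10% or more", and section 8.7.3 repeats the rule. With two or more confounders, a propensity score will be considered. Adjusted models need at least 30 events where logistic regression is used (major birth defects, SGA) and 20 where Cox regression is used (preterm delivery, spontaneous abortion, stillbirth).

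On the drug itself, section 6.1 says that in randomised trials "mepolizumab has demonstrated about a 50% reduction in asthma exacerbations" during the treatment period. Section 8.1 says that maternal asthma is associated with many adverse pregnancy outcomes.

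**The concern.** Exposure can start 8 weeks before LMP (section 8.3.1), and section 8.5 expects virtually all exposed women to have first-trimester exposure. Most of the in-pregnancy measures listed above are therefore taken after exposure has begun. The protocol supplies both links of a mediating path: the drug lowers exacerbations, and asthma is related to the outcomes.

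A mediator moves the exposure estimate just as a confounder does, so a change-in-estimate rule treats the two alike. A propensity score built on such variables has the same fault. Prenatal test results raise a different problem, because for birth defects they can be an early reading of the outcome.

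There is also a timing problem. Visits and steroid courses counted over the whole pregnancy depend on how long it lasted. A pregnancy that ends early has less time to accrue them, and for preterm delivery and pregnancy loss that length is part of the outcome.

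At stake is what an adjusted RR means: the effect of mepolizumab, or only the part that does not pass through asthma control.

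**Working it through.** **1. The plan's own figures.** Table 3 (section 8.5) uses 180 exposed and 270 unexposed asthmatic pregnancies, control risks of 3%, 7% and 10%, and α = 0.05 (taken as two-sided). The Kelsey formula is n₁ = (1.96 + 0.84)² · p̄(1 − p̄)(r + 1) / [(p₁ − p₀)² r], with r = 270/180 = 1.5. At 80% power it gives minimum RRs of 3.04, 2.17 and 1.93, which round to the stated 3.0, 2.2 and 1.9. The inputs are sound and serve for the event counts.

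**2. Which adjusted models will run?** Expected events in Cohorts 1 and 2 = 180·p₀·RR + 270·p₀. Chances are from the exact sum of two binomials.

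| Outcome | RR | Expected events | Minimum | Chance of reaching it |
|---|---|---|---|---|
| Major birth defects | 1 | 5.4 + 8.1 = 13.5 | 30 | 0.00005 |
| Major birth defects | 3 | 16.2 + 8.1 = 24.3 | 30 | 0.14 |
| SGA | 1 | 18 + 27 = 45 | 30 | 0.995 |
| Preterm delivery | 1 | 12.6 + 18.9 = 31.5 | 20 | 0.99 |

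For defects, an expected count of 30 needs RR = (30 − 8.1)/5.4 = 4.06. If the overall analysis sample means all three cohorts, and Cohort 3 also has 270 pregnancies at 3%, expected defects are 21.6 at RR 1 (chance 0.05) and 32.4 at RR 3 (chance 0.69). Multiples are excluded from SGA and preterm delivery, which lowers those counts somewhat. The protocol gives no rates for spontaneous abortion or stillbirth, so no count can be made for them.

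**3. How far can one mediator move the estimate?** Let e₀ be the exacerbation risk in Cohort 2, k the RR of the outcome given an exacerbation, and d the proportional reduction under mepolizumab. With no direct drug effect and no other confounding,

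total RR = [1 + (1 − d)·e₀·(k − 1)] / [1 + e₀·(k − 1)],

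and adjusting for exacerbations returns 1.0, a change of 1/RR − 1. Only d = 0.5 comes from the protocol (section 6.1); e₀ and k are assumptions.

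| e₀ | k | Total RR (d = 0.5) | Change on adjustment |
|---|---|---|---|
| 0.30 | 1.5 | 1.075/1.15 = 0.935 | 7.0% |
| 0.40 | 1.3 | 1.06/1.12 = 0.946 | 5.7% |
| 0.40 | 1.5 | 1.10/1.20 = 0.917 | 9.1% |
| 0.40 | 2.0 | 1.20/1.40 = 0.857 | 16.7% |
| 0.45 | 2.0 | 1.225/1.45 = 0.845 | 18.4% |
| 0.60 | 3.0 | 1.6/2.2 = 0.727 | 37.5% |

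If exposure ends early and the reduction over the whole pregnancy is only d = 0.25, the row with e₀ = 0.45 and k = 2 becomes 1.3375/1.45 = 0.922, a change of 8.4%.

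**4. How often would the rule select it?** In 4,000 simulated studies per setting (180 v 270, d = 0.5, Mantel-Haenszel RR), with e₀ from 0.30 to 0.60 and k from 1.5 to 3, an exacerbation mediator met the 10% rule in 31% to 99% of studies for SGA and 33% to 96% for preterm birth. When exacerbations had no effect on the outcome (k = 1), chance alone selected them in 7% to 28% and 12% to 37%. The simulation used risk ratios, not the planned logistic and Cox models.

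**The case against.** The best defence has four parts.

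First, section 8.3.3 covers effect modifiers as well as confounders, calls the items potential, and leaves detail to a Data Analysis Plan (DAP) not shown here. Section 8.7.3 tests only relevant confounders, and section 8.7.2 gives ACT and exacerbations an exploratory effect-modifier role. This is fair, but only in part. The DAP is promised to add detail, not to replace the stated rule, and the exploratory uses do not take these items off the candidate list.

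Second, ACT and exacerbations also stand for underlying severity, so dropping them could leave confounding by indication. This stands, and the fix allows for it.

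Third, the 50% reduction applies during treatment, and section 8.9 warns that exposure may be confined to the first weeks of pregnancy. For secondary outcomes exposure may also start late, so some early measures can precede it. Both points shrink the mediated effect for some women.

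Fourth, the primary endpoint has a crude exact comparison, and its adjusted model will seldom run.

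Three stronger readings are tempting but not supported. A reader might infer that the rule is bound to bring mediators in; several rows of the table stay below 10%, and simulated selection ranges widely. A reader might infer that the severity class counts mepolizumab, leaving the cohorts without overlap. Section 8.3.3 says only that self-reported prescriptions are classified by GINA, Table 2 lists ACT as a severity measure too, and section 8.5 has Cohort 2 spanning the severity range with emphasis on severe patients. A reader might also infer that harm will be understated. That would follow if a complication lay on a harmful path, but the documents give no figure for one.

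**Conclusion.** The concern holds as a defect in the adjusted secondary analyses. Followed as written, the plan can adjust for consequences of exposure, and nothing in sections 8.3.3, 8.7.1 or 8.7.3 prevents it. SGA and preterm delivery are the outcomes mainly affected, since their adjusted models are almost certain to run under the Table 3 assumptions. For spontaneous abortion and stillbirth the dependence on pregnancy length applies in principle, if enough events occur for an adjusted model.

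The primary endpoint is largely protected, and the prenatal-result problem is therefore mostly theoretical, unless the defect risk is several times higher or all three cohorts are pooled.

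The size, a total RR of 0.94 to 0.73 brought back to about 1.0, rests on assumed exacerbation risks and effects, on the cited 50% reduction holding across pregnancy, and on no direct effect. It shows what can happen and is not a forecast.

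**What to change.** In sections 8.3.3, 8.7.1 and 8.7.3:

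1. Limit candidates for the main adjusted model, or propensity score, to covariates fixed before LMP or first exposure: demographics, obstetric history, BMI, pre-existing conditions, early lifestyle factors and years since asthma diagnosis.
2. Add an asthma severity class built from background medication, and state explicitly that mepolizumab does not count towards it.
3. Report models that add in-pregnancy exacerbations, systemic steroids and ACT only as labelled sensitivity, mediation or effect-modifier analyses.
4. Do not adjust for pregnancy complications or prenatal test results. Keep the stratification by prenatal testing before enrolment already planned in section 8.7.2.

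Most of this is a change of wording in the protocol and DAP. The severity class may cost more. Section 8.4 describes interview data on medications taken in pregnancy, and the exposure form in Annex 2 asks for actual start dates, as opposed to the LMP date, only for certain drugs. A pre-LMP treatment step may therefore need start dates from specialist records or a new form instruction. If neither is feasible, use the enrolment class without mepolizumab. Some confounding by indication may remain in the main model, which is the reason for keeping the sensitivity model beside it.

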#### **8.4. Data sources**

*Maternal Interviews:* In all three study groups, data are collected by semi-structured maternal telephone interview on two to four occasions during and shortly after completion of pregnancy. The interviews include data on exposure timing, dose, and duration for all medications, including mepolizumab, taken anytime in pregnancy as well as data on a wide variety of confounders (See Section [8.3.3](#)).

For women exposed to mepolizumab or other asthma medications, information on disease severity/symptom control from the Asthma Control Test is obtained directly from the mother at each maternal telephone interview. In addition, information on asthma-related hospitalizations and physician visits is collected at the enrollment interview and each of the subsequent maternal interviews. At the conclusion of pregnancy, regardless of the outcome, participants are interviewed about the outcome including presence or absence of birth defects, pregnancy and infant complications and infant size. At this time point the Asthma Symptom Control test questions are asked again to reflect the last four weeks of pregnancy. In addition, asthma treatment regimen at enrollment according to GINA guidelines will be used to classify disease severity.

*Medical Records:* Mothers are asked to release medical records to the study investigators from their obstetrician or other obstetric provider, specialty care provider such as allergist/pulmonologist, hospital of delivery, pediatrician, and any other health care provider involved in the pregnancy. These records are abstracted and used to validate pregnancy outcomes and when necessary to provide details regarding timing or dose of

mepolizumab and other asthma medications in the absence of clear information from maternal report. Self-reported prescriptions used for GINA classification will be validated with medical record information where available. Pre-defined definitions for each of the study outcomes are used for classification.

Validation of classification of major birth defects, the primary outcome, is conducted periodically and before each annual and final study reports by VAMPSS Investigators, who have the relevant expertise to review the outcomes.

